### **2.2 TRIAL OBJECTIVES**

The objective of the trial is to assess the efficacy and safety of alteplase (rt-PA) in Chinese patients with acute ischemic hemispheric stroke where thrombolysis is initiated between 3 and 4.5 hours after stroke onset.

The primary efficacy outcome is functional independence as measured by the mRS (score of 0-1). It will be assessed at visit 5 ( Day 90 ) after stroke onset.

The primary safety outcome measures for the trial is symptomatic intra-cerebral haemorrhage (sICH), assessed for the whole study period centrally evaluated by DMC consultants. As for the protocol, sICH is defined as the same with ECASS III criteria, details refer to [section 5.3.1](#).

## **2.3 BENEFIT - RISK ASSESSMENT**

Stroke care quality improvement should be a continuous effort. There are established database to capture the achievement of stroke care quality improvement [[P06-03224](#), [P11-05168](#), [P07-00880](#)]. The reason for these advances was multifactorial and included improved prevention and improved care within the first hours of acute stroke, within which intravenous fibrinolytic therapy increased and it is still recommended as the first-line treatment by most national and international association [[P01-09325](#), [P07-06240](#), and [P04-01702](#)]. Its high efficacy and safety have been proved in randomized controlled clinical trials (RCTs) when the treatment is given within 3 hours after onset of neurological symptoms in selected patients with acute ischemic stroke [[P95-4908](#), [P95-3793](#), [P98-10052](#), [P00-00047](#), [P00-01176](#)]. Subsequent additional trials and analysis suggest that patient can still benefit from thrombolysis with alteplase after extending the treatment up to 4.5 [[P08-12177](#), [P08-11746](#), [P10-08848](#), [P10-05924](#)]. Overall, the results were consistent, which indicated that intravenous rtPA can be given safely to, and can improve outcomes for, carefully selected patients treated 3 to 4.5 hours after stroke.

In clinical practice, rt-PA is not always beneficial, since it sometimes fails in achieving rapid reperfusion, delivers poor recanalization rates in some vessels, and is associated with bleeding risk. For more details of reported adverse reaction of the product please refer to [appendix 10.6](#). Adverse reaction per the local approved label, dated as 29Dec 2014.

The major risk of intravenous rtPA treatment remains sICH. Although the presence of edema or mass effect on baseline CT scan was associated with higher risk of sICH, patients with these findings were more likely to have an excellent outcome if they received fibrinolytic therapy [[P97-10211](#)].

Approaches for safety management: predefine etiology criteria for some predictors. eg. mRS score, baseline NIHSS score and platelet count. 3 out of 17 clinical parameters were identified as independent predictors of sICH: prestroke mRS score (OR 1.54, P = 0.02), baseline NIHSS score (OR 1.13, P = 0.002), and platelet count (OR 0.99, P = 0.04) [[P15-10504](#)].

Given the narrow therapeutic windows of treatment of acute ischemic stroke, timely emergency department ED evaluation and diagnosis of ischemic stroke are paramount. Hospitals and EDs should create efficient processes and pathways to manage stroke patients in the ED and inpatient settings. This should include the ability to receive, identify, evaluate, treat, and/or refer patients with suspected stroke, as well as to obtain access to stroke expertise when necessary for diagnostic or treatment purposes.

All centers should be able to offer 24/7 (24 hours per day, 7 days per week) comprehensive stroke care to acute stroke patients. The hospitals must be acute stroke hospitals ready to

Proprietary confidential information © 2017 Boehringer Ingelheim International GmbH or one or more of its affiliated companies

organize effectively and efficiently evaluate, diagnose, and treat acute stroke. Besides key principle, guideline and procedures for site selection of clinical trials, the centers should fulfill below elements as,

- Ability to administer intravenous rtPA
- Ability to perform emergency brain imaging (eg, CT/MRI scan) at all times
- Ability to conduct emergency laboratory testing at all times
- Maintenance of a stroke patient notes

### **3. DESCRIPTION OF DESIGN AND TRIAL POPULATION**

#### **3.1 OVERALL TRIAL DESIGN AND PLAN**

##### **3.1.1 Administrative structure of the trial**

The trial is sponsored by

A Coordinating Investigator is responsible to coordinate Investigators at different centers participating in this multicenter trial. Tasks and responsibilities are defined in investigator agreement.

Relevant documentation on the participating (Principal) Investigators and other important participants, including their curricula vitae, will be filed in Investigator Study File (ISF).

A data-monitoring committee (DMC), independent of the sponsor will be established to assess the progress of the clinical trial, focusing on the safety outcomes for the benefit-risk evaluation at pre-specified time points, and to recommend to the sponsor whether to continue, modify, or stop the trial. DMC is constructed by three DMC members mainly monitoring the overall number of sICH events judged by investigators, and two DMC consultants for centrally evaluating sICH event. The detailed tasks and responsibilities of the DMC will be specified in a charter. The DMC will maintain written records of all its meetings.

. has appointed a Trial Clinical Monitor, responsible for coordinating all required activities, in order to

- manage the trial in accordance with applicable regulations and internal SOPs,
- direct the clinical trial team in the preparation, conduct, and reporting of the trial,
- ensure appropriate training and information of local clinical monitors (CML), Clinical Research Associates (CRAs), and Investigators of participating countries.

The organization of the trial in China will be performed by the respective local BI-organisation (Operating Unit, OPU) in accordance with applicable regulations and internal SOPs, or by a Contract Research Organisation (CRO) with which the responsibilities and tasks will be agreed and a written contract filed before initiation of the clinical trial.

Data Management and Statistics evaluation will be done by BI according to BI SOPs and CRO SOPs. The final executed contract must state the duties within the scope of work.

Tasks and functions assigned in order to organise, manage, and evaluate the trial are defined according to BI SOPs. A list of responsible persons and relevant local information can be found in the ISF.

#### **3.2 DISCUSSION OF TRIAL DESIGN, INCLUDING THE CHOICE OF CONTROL GROUP**

##### **An open label, prospective, single arm study**

Study design has been fully discussed with center of drug evaluation (CDE) in CFDA with support from several external neurologists. This study is designed as an open label single arm

study for the following reasons. The new version of Chinese Intravenous rt-PA consensus was published in 2013 regarding the usage of IV rt-PA on patients with acute ischemic stroke. The Chinese Stroke Therapy Expert Panel concluded that IV rt-PA is currently the most effective therapy and clinical evidence supports the use of IV rt-PA between 3 and 4.5 hours after the onset with several exclusion criteria. Therefore it is not ethical to design a placebo-controlled randomization study as ECASS III in China with current available evidence.

Although urokinase is recommended in Chinese guideline, it's only for patients that alteplase cannot be given.

Furthermore, patients need to be treated immediately after AIS onset. It is impractical and not ethical to randomize patients to two groups as 0-3 hours and 3-4.5 hours after AIS onset for comparison. Without randomization, it does not add much scientific value to design the study including 0-3 hours patients for the comparison and evaluation of safety and evaluation of 3-4.5 hours due to the uncontrolled confounding factors.

### **3.3 SELECTION OF TRIAL POPULATION**

A log of all patients enrolled into the trial (i.e. who have signed informed consent) will be maintained in the ISF at the investigational site irrespective of whether they have been treated with investigational drug or not.

#### **3.3.1 Main diagnosis for trial entry**

Please refer to [section 8.3.1](#) (Source Documents) for the documentation requirements pertaining to the in- and exclusion criteria.

#### **3.3.2 Inclusion criteria**

1. Age  $\geq 18$  years at screening (visit 1A) but  $\leq 80$  years
2. Male or female patients. Women of childbearing potential must be ready and able to use highly effective methods of birth control per ICH M3 (R2) that result in a low failure rate of less than 1% per year when used consistently and correctly. A list of contraception methods meeting these criteria is provided in the patient information
3. Signed and dated written informed consent in accordance with GCP and local legislation prior to admission to the trial
4. Diagnosis of ischemic stroke with a measurable neurological deficit on National Institute of Health Stroke Scale (NIHSS)

Stroke symptoms should have been present for at least 30 minutes without significant improvement prior treatment

5. Thrombolytic therapy can be initiated within 3 to 4.5 hours of stroke onset
6. Willingness and ability to comply with protocol

#### **3.3.3 Exclusion criteria**

1. Stroke onset  $>4.5$  hours prior to infusion start or when time of symptom onset is unknown

2. Evidence of intracranial haemorrhage (ICH) on the CT/MRI-scan or symptoms suggestive of subarachnoid haemorrhage, even if the CT/MRI-scan is normal
3. Patients who must or wish to continue the intake of restricted medications (see [section 4.2.2.1](#)) or any drug considered likely to interfere with the safe conduct of the trial
4. Acute bleeding diathesis, including but not limited to
  - a. Known genetic predisposition to bleeding or significant bleeding disorder at present or within the past 6 months
  - b. Administration of heparin within the previous 48 hours and aPTT exceeding the upper limit of normal for laboratory
  - c. Platelet count of below 100,000/mm^3
  - d. Taking oral anticoagulant
  - e. Any history of central nervous system damage (i.e. neoplasm, aneurysm, intracranial or spinal surgery)
  - f. Recent traumatic external heart massage, obstetrical delivery, within the past 10 days, recent puncture of a non-compressive blood-vessel (e.g subclavian or jugular vein puncture)
  - g. Known history of suspected intracranial haemorrhage or suspected subarachnoid haemorrhage from aneurysm
  - h. Neoplasm with increased hemorrhagic risk
  - i. Documented ulcerative gastrointestinal disease during the last 3 months, oesophageal varices, arterial-aneurysm, arterial/venous malformations
  - j. Any known disorder associated with a significant increased risk of bleeding
5. Bacterial endocarditis, pericarditis
6. Acute pancreatitis
7. Severe hepatic dysfunction, including hepatic failure, cirrhosis, portal hypertension (oesophageal varices) and active hepatitis
8. Significant trauma or major surgery (according to the investigator's assessment) in past 3 months
9. Severe stroke as assessed clinically (e.g. NIHSS>25) and/ or imaging demonstrates multi-lobar infarction (hypodensity >1/3 cerebral hemisphere)
10. Minor neurological deficit or symptoms rapidly improving before start of infusion
11. Severe uncontrolled arterial hypertension, e.g. systolic blood pressure>185 mmHg or diastolic blood pressure>110mmHg, or aggressive management (IV medication) necessary to reduce BP to these limits
12. Blood glucose <50 mg/dL or >400 mg/dL
13. Any history of prior stroke in previous 3 months, or any history of prior stroke with concomitant diabetes
14. Seizure at stroke onset
15. Known hypersensitivity to active substance alteplase, gentamicin (a trace residue from the manufacturing process) or to any of the excipients.
16. Currently enrolled in another investigational device or drug study, or less than 30 days since ending another investigational device or drug study(s), or receiving other investigational treatment(s)
17. Women who are pregnant, nursing, or who plan to become pregnant while in the trial

### **3.3.4 Removal of patients from therapy or assessments**

#### **3.3.4.1 Removal of individual patients**

An excessive withdrawal rate can have a severe negative impact on the scientific value of the trial. Every effort should be made to keep patients in the trial as scheduled. This includes careful patient selection and appropriate explanation of the trial requirements and procedures prior to enrolment as well as an explanation of the consequences of premature withdrawal.

An individual patient is to be withdrawn from trial treatment if:

- The patient withdraws consent for trial treatment or trial participation, without the need to justify the decision.
- The patient needs to take concomitant drugs that interfere with the investigational product or other trial medication
- The patient, who had discontinued the treatment for any reasons (such as surgery, adverse events, other diseases), can no longer be treated with trial medication again. The patient has repeatedly shown to be non-compliant with important trial procedures and, in the opinion of both, the investigator and sponsor representative, is not willing or able to stick to the trial requirements in the future.

Given the patient's agreement, the patient will undergo the procedures for early treatment discontinuation and follow up as outlined in the [Flow Chart](#).

For all patients the reason for withdrawal (e.g. adverse events) must be recorded in the CRF. These data will be included in the trial database and reported.

#### **3.3.4.2 Discontinuation of the trial by the sponsor**

Boehringer Ingelheim reserves the right to discontinue the trial overall or at a particular trial site at any time for the following reasons:

1. Failure to meet expected enrolment goals overall or at a particular trial site
2. Emergence of any efficacy/safety information invalidating the earlier positive benefit-risk-assessment that could significantly affect the continuation of the trial
3. Violation of GCP, the CTP, or the contract disturbing the appropriate conduct of the trial

The Investigator / the trial site will be reimbursed for reasonable expenses incurred in case of trial termination (except in case of the third reason).

## **4. TREATMENTS**

### **4.1 INVESTIGATIONAL TREATMENTS**

#### **4.1.1 Identity of the Investigational Medicinal Products**

Table 4.1.1: 1                   Test product: Alteplase

Substance:	Alteplase (rt-PA)
Brand name:	Actilyse®
Pharmaceutical formulation:	Lyophilisate and solvent for injection The powder is presented as a colourless to pale yellow lyophilizate cake
Source:	BI Pharma GmbH & Co. KG
Unit strength:	50mg
Posology	Actilyse® 50 mg, vial containing 50 mg Alteplase lyophilisate plus vial of solvent containing 50 mL sterile water for injection. The reconstituted solution contains 1 mg alteplase per mL.
Route of administration:	IV

Under aseptic conditions the content of injection vial of Alteplase lyophilisate (50mg) dry substance is dissolved with 50ml sterile water for injection to obtain a final concentration of 1mg alteplase per mL.

For this purpose a transfer cannula should be managed at each site. When reconstituting the product from the respective amount of powder and solvent, the mixture should only be agitated gently until complete dissolution. Any vigorous agitation should be avoided to prevent foam formation.

The reconstituted preparation is a clear and colourless to pale yellow solution. Prior to administration it should be inspected visually for particles and colour. It may be diluted further with sterile sodium chloride 9 mg/mL (0.9%) solution for injection up to a minimal concentration of 0.2 mg/mL.

A dilution of the reconstituted solution with sterilised water for injections or in general, the use of carbohydrate infusion solutions, e.g. dextrose is not used.

Actilyse® should not be mixed with other drugs, neither in the same infusion-vial nor the same venous line.

#### **4.1.2 Dosage and treatment schedule**

The study drug will be administered as a total single dose of 0.9 mg/kg per patient. The upper dose limit is set to 90 mg per patient. Ten percent of the total dose will be administered as a bolus over 1 - 2 minutes. The remaining 90% of the dose will be given by continuous IV infusion over 60 minutes if there is no evidence of an allergic reaction within 5 minutes following the administration of the test dose.

The dose is weight adjusted, therefor investigator should try every effort to take the actual body weight of the patient. If it is hard to have an actual body weight due to certain reasons, an estimated body weight by investigator is acceptable.

The treatment effect is time-dependent; therefore earlier treatment increases the probability of a favourable outcome [[P08-12177](#)], so patients eligible in the 3-4.5 hrs time window should be treated without delay.

#### **4.1.3 Method of assigning patients to treatment**

It is an open label trial.

At visit 1A, after assessment of all in- and -exclusion criteria, each eligible patient will be assigned with medication manually. Site personnel will enter the medication number in the CRF.

#### **4.1.4 Blinding and procedures for unblinding**

It is an open label trial. Blinding concern and unblinding procedure are not applicable for this trial.

#### **4.1.5 Packaging, labelling, and re-supply**

The investigational products will be provided by Clinical Trial Supply Unit (CTSU). They will be packaged and labelled in accordance with the principles of Good Manufacturing Practice (GMP).

The clinical trial supply kit consists of two vials of alteplase lyophilisate and two vials of sterile water. Details of packaging and description of the label will be provided in the ISF.

Initial supply and further re-supplies will be managed by an IRT, inventory needs to be monitored/maintained manually. To facilitate the use of the IRT, the investigator will receive all necessary instructions for using the IRT. Details please refer to user manual in the ISF.

#### **4.1.6 Storage conditions**

Drug supplies will be kept in their original packaging and in a secure limited access storage area according to the recommended storage conditions on the medication label. The vials have to be stored at room temperature (not above 25°C) and have to be protected from light. Freeze is not allowed. A temperature log must be maintained for documentation.

If the storage conditions are found to be outside the specified range, the local clinical monitor (as provided in the list of contacts) must be contacted immediately.

#### **4.1.7 Drug accountability**

The Investigator and/or Pharmacist will receive the investigational drugs delivered by the sponsor when the following requirements are fulfilled:

- Approval of the trial protocol by the IRB / ethics committee
- Availability of a signed and dated clinical trial contract between the sponsor and the head of the investigational site,
- Approval/notification of the regulatory authority, e.g. competent authority,
- Availability of the curriculum vitae of the principal Investigator,
- Availability of a signed and dated clinical trial protocol
- Availability of the proof of a medical license for the principal Investigator

The Investigator and/or Pharmacist must maintain records of the product's delivery to the trial site, the inventory at the site, the use by each patient, and the return, including the unused product returned back to local depot. If applicable, the sponsor and the distributional partner will maintain records of the disposal.

These records will include dates, quantities, batch / serial numbers, expiry ('use- by') dates, and the unique code numbers assigned to the investigational product and trial patients. The Investigator / Pharmacist / investigational drug storage manager will maintain records that document adequately that the patients were provided the doses specified by the CTP and reconcile all investigational products received from the sponsor. All used product will be destructed at sites. All unused products will be return to the local depot. At the time of return the Investigator / Pharmacist must verify that no remaining supplies are in the Investigator's possession.

#### **4.2 OTHER TREATMENTS, EMERGENCY PROCEDURES, RESTRICTIONS**

##### **4.2.1 Other treatments and emergency procedures**

Actilyse should be used by physician experienced in the use of thrombolytic treatment and with the facilities to monitor that use. As with other thrombolytics, it is recommended that when Actilyse is administered, standard resuscitation equipment and medication be available in all circumstances.

Recommendation of managing bleeding

The most common complication encountered during Actilyse therapy is bleeding. The concomitant use of heparin anticoagulation may contribute to bleeding. As fibrin is lysed during Actilyse therapy, bleeding from recent puncture sites may occur. Thrombolytic therapy requires careful attention to all possible bleeding sites (including those following catheter insertion, arterial and venous puncture cutdown and needle puncture). The use of rigid catheters, intramuscular injections and non-essential handling of the patient should be avoided during treatment with Actilyse.

Should serious bleeding occur, in particular cerebral haemorrhage, the fibrinolytic therapy must be discontinued and concomitant heparin administration should be terminated

immediately. Administration of protamine should be considered if heparin has been administered within 4 hours before the onset of bleeding. In the few patients who fail to respond to these conservative measures, judicious use of transfusion products may be indicated.

Transfusion of cryoprecipitate, fresh frozen plasma, and platelets should be considered with clinical and laboratory reassessment after each administration. A target fibrinogen level of 1 g/L is desirable with cryoprecipitate infusion. Antifibrinolytic agents should also be considered.

#### Recommendation of managing hypersensitivity

No sustained antibody formation to the recombinant human tissue-type plasminogen activator molecule has been observed after treatment. There is no systematic experience with re-administration of Actilyse. Anaphylactoid reactions associated with administration of Actilyse are rare.

If an anaphylactoid reaction occurs, the infusion should be discontinued and appropriate treatment should be initiated. Monitoring is recommended particularly for patients receiving ACE-inhibitors concomitantly.

#### Recommendation of managing other AEs

During and following a subject's participation in a trial, the investigator should ensure that adequate medical care is provided to a subject for any adverse events, including clinically significant laboratory values, related to the trial.

### **4.2.2      Restrictions**

#### **4.2.2.1      Restrictions regarding concomitant treatment**

Additional thrombolytic medication (e.g. urokinase or streptokinase) is forbidden. Heparin: In exceptional circumstances, low dose subcutaneous heparin may be given concomitantly during the first 24 hours in order to prevent deep venous thrombosis provided that the aPTT will not be prolonged for more than 2 times over the baseline value. APTT must be determined regularly during the subcutaneous (SC) administration of heparin. The SC heparin dose must not exceed 10,000 IU of sodium heparin during 24 hours or equivalent doses of low molecular weight heparin. Simultaneous administration of heparin and other antithrombotic drugs is strongly discouraged.

IV heparin at any dose is forbidden before and during the study drug administration and during the initial 24 hours after completion of administration of study drug.

Thereafter intravenous heparin must not be started before the second CT is evaluated and reveals no signs of intracranial bleeding.

Other medication:

Administration of oral anticoagulants, antiplatelet agents (i.e. aspirin), hemorrhheologic agents, and brain protective drugs (e.g. calcium channel blockers) is prohibited during the first 24 hours after completion of the study drug administration.

The use of volume expanders, such as dextran and hydroxyethyl starch, is prohibited within the first 24 hours after completion of study drug infusion.

Traditional Chinese medicine which had been demonstrated with evidence of effect as anticoagulants, antiplatelet agent, hemorrhheologic agents and brain protective agents is prohibited during the first 24 hours after completion of the study administration [P14-16668](#).

Other drug therapy may be given according to patient needs. Osmotic agents (mannitol, glycerol) may be given if the intracranial pressure is increased.

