### **6.2.3      Observation Period and Trial Completion**

A physical examination, the documentation of adverse events and of concomitant medication will be performed for all patients at all predefined treatment time points (Visit 1B and Visit 1C) as of the administration day and visit 2,3,4, and 5.

Lab test at visit 1A and visit 3 are mandatory. It will be optional at visit 2 and visit 5 in case of clinical deterioration (considered by investigator)

At visit 1B (i.e., 1 hour after the start of infusion of study drug), vital signs will be measured every 30 minutes until Hour 2. An 12-lead ECG recording will be made.

At visit 1C (i.e., 2 hours after the start of infusion of study drug), the NIH Stroke Scale will be performed. Vital signs will be measured every 30 minutes for 6 hours, then hourly until 24 hours. An 12-lead An 12-lead ECG recording will be made.

At visit 2 (24 hours), vital signs will be measured. The NIH Stroke Scale will be performed. A second imaging (CT/MRI) scan will be done within Hour 22 and Hour 36 after start of infusion of study drug.

At visit 3 (on day 7), vital signs will be measured. The NIH Stroke Scale will be performed. An 12-lead ECG recording will be made. A CT/MRI scan will be performed in case of clinical deterioration

At visit 4 (on day 30), vital sign will be measured. The NIH Stroke Scale, the modified Rankin Scale, and the Barthel Index will be performed. A CT/MRI scan will be performed in case of clinical deterioration.

At visit 5 (on day 90), vital sign will be measured. The NIH Stroke Scale, the Glasgow Outcome Score, the modified Rankin Scale, and the Barthel Index will be performed. A physical examination takes place. The patient termination record will be filled in. Length of stay in hospital will be assessed as well.

The trial completion (end of the trial) eCRF page has to be filled-in when patient has terminated the trial.

The end of the trial is:

- At the end of visit 5(Day 90 per protocol) for patients who have completed the trial on treatment and came to future visits as planned.
- After early discontinuation, if a patient refuses to attend future visits as originally planned.

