## **6.3 VISIT WINDOW AND TRIAL COMPLETION**

### **6.3.1 Visit schedule**

For visit 1A (D0) there is no time window.

For visit 1B, a window between +15 and - 15 minutes is acceptable.

For visit 1C, a window between +30 and -30 minutes is acceptable.

For visit 2 (D1), a window between +2 and -2 hours is acceptable. The second cerebral CT/MRI may be done between Hour 22 and Hour 36 after start of infusion of study drug.

For visit 3 (D7), a window between +3 and -3 days is acceptable.

Visit 4 (D30) may take place between 27 and 33 days.

Visit 5 (D90) may take place between 83 and 97 days.

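### Oral anticoagulants, antiplatelet agents and similar traditional Chinese medicines may start before the second scan is read, although IV heparin may not (minor patient-safety point)

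*Protocol*

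**What the plan says.** Protocol 4.2.2.1 grades its restrictions by agent.

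- **IV heparin** has two conditions. It is banned until 24 hours after study drug is complete, and then: "Thereafter intravenous heparin must not be started before the second CT is evaluated and reveals no signs of intracranial bleeding".
- **Oral anticoagulants and antiplatelet agents** have one condition: "Administration of oral anticoagulants, antiplatelet agents (i.e. aspirin), hemorrhheologic agents, and brain protective drugs (e.g. calcium channel blockers) is prohibited during the first 24 hours". The 24 hours run from completion of study drug, and no scan condition follows.
- **Traditional Chinese medicines with comparable effects** have the same single condition: "Traditional Chinese medicine which had been demonstrated with evidence of effect as anticoagulants, antiplatelet agent, hemorrhheologic agents and brain protective agents is prohibited" for the same 24 hours.
- **Low-dose subcutaneous heparin** may be given exceptionally within the first 24 hours, under aPTT and dose limits and without a scan.

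The timing comes from three other places. On the infusion, Protocol 4.1.2 states: "The remaining 90% of the dose will be given by continuous IV infusion over 60 minutes". Protocol 6.2.3 places the second scan in its visit 2 paragraph, which opens "At visit 2 (24 hours), vital signs will be measured" and goes on: "A second imaging (CT/MRI) scan will be done within Hour 22 and Hour 36 after start of infusion of study drug". Protocol 6.3.1 gives two separate windows: "For visit 2 (D1), a window between +2 and -2 hours is acceptable", and for the scan, "The second cerebral CT/MRI may be done between Hour 22 and Hour 36 after start of infusion of study drug". Footnote 3 of the Flow Chart repeats the 22 to 36 hour scan window.

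In the SAP, violation code D1 in Table 6.2:1 only points back to Protocol 4.2.2. SAP 7.2 summarises all concomitant therapy up to Visit 5 and tabulates antithrombotics separately only for the first 24 hours after the start of bolus.

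**The concern.** Protocol 2.3 names sICH as the main risk of the treatment, and the second scan is the scheduled check for bleeding. For IV heparin the protocol insists on seeing that scan first. For oral anticoagulants, antiplatelet agents and the corresponding traditional medicines it does not, although exclusion criterion 4 in Protocol 3.3.3 itself counts oral anticoagulant use under bleeding diathesis.

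At stake is mainly the patient with a bleed that gives no clinical signs, who receives a first dose of such an agent shortly before a scan that would have shown it. A dose of this kind would comply with the protocol and would not count as a violation under code D1. It would appear in the overall concomitant-therapy summary, but nothing there would show that it came before the scan. The separate antithrombotic table stops too early to include it.

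**Working it through.** The plan states no figure for this gap, so there is none to reproduce. The check is clock arithmetic, in hours after infusion start.

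**Inputs**

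| Input | Value | Source |
|---|---|---|
| Infusion length | 1 h | Protocol 4.1.2 |
| Ban on the agents | 24 h after completion of study drug | Protocol 4.2.2.1 |
| Visit 2 window | 24 ± 2 h, i.e. 22 to 26 h | Protocol 6.3.1 |
| Permitted scan window | 22 to 36 h | Protocol 6.2.3, 6.3.1, Flow Chart footnote 3 |

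**Formulas**

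End of ban = infusion length + 24 h = 1 + 24 = 25 h.

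Gap = max(0, scan time − end of ban), plus the time needed to read the scan if it is not read by the end of the ban.

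**Results for a full infusion**

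| Scan time | Gap before reading time |
|---|---|
| 22 h | 0 h |
| 24 h | 0 h |
| 26 h (end of visit 2 window) | 26 − 25 = 1 h |
| 36 h (latest permitted) | 36 − 25 = 11 h |

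The part of the visit 2 window after the ban ends is 26 − 25 = 1 of 4 hours. The part of the permitted scan window after the ban ends is 36 − 25 = 11 of 14 hours. These are shares of a window, not of patients.

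**Sensitivity**

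- *Counting from the start of the bolus.* The infusion then ends about 1.03 to 1.12 h after time zero. The gaps are about 0.9 to 1.0 h for a scan at 26 h and 10.9 to 11.0 h for a scan at 36 h.
- *Infusion stopped early.* If stopping counts as completion, the ban ends sooner. For an infusion stopped at 0.1 h (6 minutes), the ban ends at 24.1 h. The gap is 26 − 24.1 = 1.9 h at the end of visit 2 and 36 − 24.1 = 11.9 h at the limit.

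**The SAP table.** The separate antithrombotic summary ends 24 h after bolus start, about 1 h before the ban ends (25 − 24). It therefore misses the whole interval in question.

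**The case against.** The strongest reply is that the grading looks deliberate. Protocol 4.2.1 singles out concomitant heparin as a contributor to bleeding, requires it to be stopped at once in serious bleeding and adds protamine guidance. No comparable visible statement concerns aspirin or traditional medicines. The protocol also tolerates low-dose subcutaneous heparin before the scan.

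Other safeguards narrow the exposure. Patients taking oral anticoagulants, or who must or wish to continue restricted medication, are excluded (Protocol 3.3.3, criteria 4d and 3), so the gap concerns mainly new starts. Patients are watched in a stroke unit or ICU (5.3), NIHSS is scored at 24 hours (5.2), and treating physicians must be experienced in thrombolysis (4.2.1). On the visit 2 schedule the gap is an hour at most for a full infusion, before reading time.

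There is also an objection to the obvious remedy. If the heparin condition were simply copied across, a patient whose scan shows any bleeding, or was missed, would never meet it and would be barred for the rest of the 90-day trial. The label text in Appendix 10.6 gives intracerebral haemorrhage in up to 15% of stroke patients. If that ceiling applied here, it would be 0.15 × 120 = 18 patients.

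Much of this stands. The text on heparin partly explains a stricter heparin rule, the exposure is small, and any remedy needs a release rule. But a reason to be strict with heparin does not show that the other agents are safe before the scan. Clinical monitoring and NIHSS detect deterioration, not a silent bleed. No visible passage closes the gap.

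**Conclusion.** The difference between the rules is real and unclosed, and it is a minor patient-safety point. A first dose of these agents before the second scan is permitted: 0 to about 1 h early on the visit 2 schedule, about 11 h plus reading time at the 36 h limit, and nearly 12 h if the infusion is stopped early. The first two figures assume a full 60-minute infusion. The last assumes that stopping counts as completion.

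A reader might infer more than the documents support:

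- *That the rules conflict, or that early dosing is instructed.* All the rules can be obeyed together, and a site may wait for the scan.
- *That an 11-hour gap is typical, or that 11 in 14 patients are exposed.* The documents give no distribution of scan times, and the scan is listed under visit 2. The number of patients affected is unknown.
- *That these agents carry the same risk as IV heparin.* The documents do not compare the risks.
- *That the sICH estimate is distorted.* Nothing in the documents allows such an effect to be derived, and none is claimed.

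**What to change.** In Protocol 4.2.2.1, state that oral anticoagulants, antiplatelet agents and traditional Chinese medicines with evidence of anticoagulant or antiplatelet effect may not be started until both conditions are met: 24 hours have passed since completion of study drug, and the second CT/MRI has been evaluated. If the scan shows no intracranial bleeding, they may start. If it shows bleeding or was not done, starting is left to the investigator's documented benefit-risk judgement, with repeat imaging only if clinically indicated. That release rule avoids an open-ended ban. Leave the subcutaneous heparin exception and the other listed agents unchanged.

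Optionally, in SAP 7.2, extend the separate antithrombotic summary from 24 h to 36 h after the start of bolus. That would bring the doses in question into the table, although scan times would still be needed to show which doses came first.

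The cost is a short protocol addition and, if wanted, a wider window for one table. No procedure is added, because the scan is already scheduled for every patient. The clinical downside is a later first dose: 0 to about 1 h if the scan is done at visit 2, and at most about 11 to 12 h, plus reading time. The documents give no figure for the harm of such a delay. Sites can avoid it by scanning and reading at hours 22 to 25, which the present window allows. For patients with bleeding on the scan, or no scan, the start depends on the investigator's decision.
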